### **Sensitivity analysis:**

Three sensitivity analyses will be performed to assess the robustness of the results generated for the primary efficacy analysis.

#### Analysis of Treatment Policy Estimand

Sensitivity analysis of the treatment policy estimand for the co-primary endpoints will be performed using similar analysis methods as the primary efficacy analysis. The treatment policy estimand is the difference in means between each fasinumab dose and placebo in the change from baseline to week 16 in the WOMAC pain and physical function scores in the mFAS, regardless of study treatment discontinuation prior to week 52 and regardless of whether or not

rescue medication or prohibited medication had been taken. Hence, data from all patients, including data collected after discontinuing treatment up to week 52 will be used in this sensitivity analyses. Missing WOMAC subscale scores up to week 52 will be imputed with the same approach used in the primary analysis.

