### 5.7.1. Analysis of Primary Efficacy Variables

The co-primary efficacy variables are:

1. Change in the WOMAC pain subscale scores from baseline to week 16
2. Change in the WOMAC physical function subscale score from baseline to week 16

The following hypotheses will be tested:

- $H_{1,1}$ : There is no treatment difference between fasinumab 1 mg Q4W and placebo in WOMAC pain or physical function subscale at week 16 versus there is treatment difference in WOMAC pain and physical function subscale score at week 16
- $H_{2,1}$ : There is no treatment difference between fasinumab 1 mg Q8W and placebo in WOMAC pain or physical function subscale at week 16 versus there is treatment difference in WOMAC pain and physical function subscale score at week 16

For  $H_{1,1}$ , the estimand is the difference in means between the fasinumab 1 mg Q4W dose and placebo in the change from baseline to week 16 in the WOMAC pain and physical function scores in the mFAS, regardless of whether or not rescue medication or prohibited medication had been taken. Any data collected after discontinuing treatment in Year 1 will not be used in the primary efficacy analysis but used in a treatment policy sensitivity analysis.

The co-primary efficacy variables will be analyzed separately using a multiple imputation approach with a mixed-effect model for repeated measures (MMRM) based on the mFAS. For patients who permanently discontinued treatment due to lack of efficacy, death or AEs, their missing WOMAC subscale scores after discontinuation will be imputed with values centered at the mean baseline WOMAC subscale score of the treatment group that patient was randomized to. For patients who discontinued treatment due to other reasons (including discontinuation because of public health measures implemented in response to COVID-19), their missing WOMAC subscale scores after discontinuation will be imputed under the missing-at-random assumption using the regression method with adjustment for covariates including treatment group, randomization strata (K-L category [2 to 3, or 4], index joint [knee, hip], and geographical region [Europe, North America]) and baseline WOMAC subscale score. Intermittently missing WOMAC subscale scores prior to treatment discontinuation will be imputed using the Markov Chain Monte Carlo method.

Missing data up to week 52 will be imputed 50 times to generate 50 complete data sets by using the SAS procedure PROC MI following the 3 steps below:

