- Step 1: The monotone missing pattern is induced by Markov Chain Monte Carlo (MCMC) method in MI procedure using seed number 4751611. If a randomly imputed score is imputed outside the range of the WOMAC subscale score of 0-10, then the algorithm will continue to randomly impute scores until one within the range of 0-10 is obtained.
- Step 2: The missing WOMAC subscale scores at visits subsequent to treatment discontinuation will be imputed using the regression method for the monotone pattern with seed number 4751611 and adjustment for covariates including treatment groups, randomization strata (K-L category [2 to 3, or 4], index joint [knee, hip], and geographical region [Europe, North America]), baseline WOMAC subscale score and

- all WOMAC subscale scores at preceding visits. Scores that are imputed outside the range of the WOMAC subscale will be addressed in the same manner as in step 1.
- Step 3: For patients who permanently discontinued study treatment due to lack of efficacy, death or AEs, the initially missing and now imputed WOMAC subscale scores at visits subsequent to treatment discontinuation will be adjusted to be centered at the mean baseline value for that treatment group, i.e., imputed score = initial imputed score under MAR – (mean change from baseline subscale score at the post-baseline time point for the treatment group based on patients on treatment with non-missing data at that time point).

Each imputed data set will be analyzed using a MMRM with terms for baseline WOMAC subscale score, randomization strata (K-L category [2 to 3, or 4], index joint [knee, hip], and geographical region [Europe, North America]), treatment, visit, and treatment-by-visit interaction as fixed effects. The MMRM will be fitted using the MIXED procedure in Statistical Analysis System (SAS) with an unstructured covariance matrix to model the within-patient errors. The denominator degrees of freedom will be estimated using Kenward-Roger's approximation. In the event a model cannot be fit due to the estimation algorithm failing to converge, the covariance matrix for within-patient errors will be modeled by an autoregressive 1 structure, followed by a compound symmetry structure if convergence is still not achieved for the prior.

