- H2,11: There is no treatment difference between fasinumab 1 mg Q8W and placebo in the WOMAC physical function subscale scores averaged across Weeks 4, 8, 12 and 16 versus there is treatment difference in the WOMAC physical function subscale scores averaged across Weeks 4, 8, 12 and 16
- H2,12: There is no treatment difference between fasinumab 1 mg Q8W and placebo in the WOMAC pain subscale scores averaged across Weeks 36, 40 and 44 versus there is treatment difference in the WOMAC pain subscale scores averaged across Weeks 36, 40 and 44
- H2,13: There is no treatment difference between fasinumab 1 mg Q8W and placebo in the WOMAC physical function subscale scores averaged across Weeks 36, 40 and 44 versus there is treatment difference in the WOMAC physical function subscale scores averaged across Weeks 36, 40 and 44

The hypotheses H1,4, H1,5, H1,6, H1,7, H1,14 and H1,15 can be tested within the same analysis method used to test H1,1 as described in Section 5.7.1. Similarly, H2,4, H2,5, H2,6 and H2,7 can be tested within the same analysis methods used to test H2,1 as described in Section 5.7.1. Additionally, the treatment policy analysis, per-protocol analysis and subgroup analyses described in Section 5.7.1 for the primary endpoint can also be utilized for the hypotheses mentioned in this paragraph.

To test H1,2, H1,8 and H1,9, a method analogous to that used to test H1,1 in Section 5.7.1 can be utilized, replacing the respective WOMAC subscale score with the PGA score. Likewise, H2,2, H2,8 and H2,9 can be tested using a method analogous to that used to test H2,1 in Section 5.7.1, replacing the respective WOMAC subscale score with the PGA score and only using the subset of patients in the mFAS randomized after protocol amendment 5 for the analyses. The multiple imputation algorithm will be modified to resample values outside the range of the PGA score (0-5) in a manner similar to the primary analysis.

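### The treatment policy sensitivity analysis imputes missing off-drug scores with the primary rule, so where those scores are missing it partly repeats the primary assumption

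*SAP*

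**What the plan says.** SAP 5.7.1 defines the treatment policy estimand as the difference in mean change to Week 16 "regardless of study treatment discontinuation prior to week 52", and also regardless of rescue or prohibited medication. It states that "data collected after discontinuing treatment up to week 52 will be used in this sensitivity analyses". For what is still missing, "Missing WOMAC subscale scores up to week 52 will be imputed with the same approach used in the primary analysis".

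The primary approach, in the same section, was built for a different dataset: "Any data collected after discontinuing treatment in Year 1 will not be used in the primary efficacy analysis". It has two branches.

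- Stops for lack of efficacy, death or adverse events: missing scores are "imputed with values centered at the mean baseline WOMAC subscale score of the treatment group that patient was randomized to". Step 3 does this by subtracting the arm's mean change among patients still on treatment.
- Stops for any other reason, explicitly including COVID-19 public health measures: imputed as missing at random. Step 2 reads "The missing WOMAC subscale scores at visits subsequent to treatment discontinuation will be imputed using the regression method for the monotone pattern". Its covariates are treatment group, randomization strata, baseline score and all preceding scores. Whether a score was obtained on or off drug is not among them.

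SAP 5.7.3 carries the analysis to the Week 44 and naproxen WOMAC comparisons: "the treatment policy analysis, per-protocol analysis and subgroup analyses described in Section 5.7.1 for the primary endpoint can also be utilized". Protocol 10.4.3.1 describes a similar method and gives no separate rule for missing off-drug scores. Protocol 7.3.2 encourages patients who stop drug to stay in the study, so some off-drug scores will be observed and some will not.

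**The concern.** For a patient who stops drug and then leaves, the treatment policy target is the score that patient would have off drug. Neither branch aims at that.

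In Step 2, retrieved off-drug scores enter the regression, but unmarked. They are pooled with a much larger body of on-drug scores, so the prediction for a fasinumab patient who has left stays near the on-drug mean. In Step 3, the shift is the on-treatment mean change, although in this analysis the Step 2 values being shifted come from a regression that also contains off-drug scores. The two no longer match, and the result need not centre on baseline.

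A treatment policy estimate that agrees with the primary will be read as evidence that the effect survives stopping drug. Where off-drug scores are missing, part of that agreement is assumed. The other two sensitivity analyses do not fill the gap. The SAP tipping point adds its delta only for stops due to adverse events, death or lack of efficacy, so stops for other reasons remain missing at random at every delta. The per-protocol set (SAP 3.3) requires all doses to Week 16 and so excludes early stoppers.

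**Working it through.** **Inputs from the plan (SAP 2.2).** Q4W 840, placebo 280; difference 1.1, SD 2.4, effect size 0.46; two-sided alpha 0.025; dropout 15% to Week 16 and 30% to Week 52.

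**The plan's own figure.** At Week 16, 840 × 0.85 = 714 and 280 × 0.85 = 238. The noncentrality is 0.46 × √(714 × 238 / 952) = 0.46 × 13.36 = 6.15, and power is Φ(6.15 − 2.24), above 99.9%. At Week 52 (588 and 196) it is 99.96%. Both agree with the stated value of at least 99%.

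**Bias formula.** Let d be the share who stop, w the share of those with missing off-drug scores, r the share stopping for other reasons, and k the fraction of drug benefit kept off drug. Take all as equal in the two arms. As fractions of the on-drug effect:

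- true treatment policy effect = (1 − d) + d·k
- planned estimate = (1 − d) + d(1 − w)k + d·w·r
- bias = d·w·(r − k)

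The second line treats Step 2 as giving full on-drug benefit. It treats Step 3 as contributing no difference, because both arms are moved to baseline. The documents do not give w, r or k.

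**Simulation check.** The SAP's sequential regression and Step 3 shift were run on 200,000 patients per arm and four visits, with retrieved off-drug scores included. Assumptions: 15% stop in each arm, placebo change −1.5, visit correlation 0.7, benefit fully lost off drug (k = 0), retrieval at random. The Step 1 MCMC and the 0–10 range resampling were left out. Bias in points, positive favouring fasinumab, formula (× 1.1) / simulation:

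| Off-drug scores retrieved | All stops other reasons | Half other reasons | None other reasons |
|---|---|---|---|
| 0% | 0.165 / 0.173 | 0.083 / 0.083 | 0 / −0.003 |
| 25% | 0.124 / 0.120 | 0.062 / 0.060 | 0 / −0.006 |
| 50% | 0.083 / 0.071 | 0.041 / 0.034 | 0 / −0.009 |
| 75% | 0.041 / 0.037 | 0.021 / 0.019 | 0 / −0.006 |

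The simulated bias falls a little below the formula once scores are retrieved, because they do pull the Step 2 regression. The pull is weak. Fasinumab patients with missing off-drug scores had a true mean change of about −1.5 and an on-drug mean of −2.6, and Step 2 imputed −2.45 to −2.63. Step 3 gave −0.02 to +0.14 rather than exactly zero.

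**How much agreement is built in.** With half other reasons and 50% retrieved, the simulated primary estimate was −1.026, the treatment policy estimate −0.982 and the truth −0.948. The analysis closes 0.044 of a 0.078 gap. With nothing retrieved it matches the primary (−1.022 against −1.020; truth −0.938).

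**Other cases.**

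- Half the benefit kept and half of stops for other reasons: r − k = 0; simulated bias 0.004 against fasinumab.
- k = 0.5, r = 0.25, w = 1: 0.15 × (−0.25) × 1.1 = −0.04, so the sign reverses.
- 20% of placebo and 12% of fasinumab patients stopping, half for other reasons, k = 0: 0.09 at 25% retrieved and 0.06 at 50%.

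**Effect on the main contrast.** At a difference of 0.93 (the approximate true value with benefit fully lost), 714 against 238 patients and SD 2.4 give 0.3875 × 13.36 − 2.24 = 2.94, a power of about 99.8% at two-sided 0.025.

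**The case against.** Any analysis must assume something about scores nobody observed, and an assumption one would not choose does not void the estimand. Observed off-drug scores are used. Patients who stop are asked to attend all remaining visits. No alpha depends on this analysis, because the hypotheses are decided on the primary. All of that stands, and it keeps the point modest.

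Three stronger readings are tempting, and the documents do not support them.

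- A reader might infer that retrieved off-drug scores have no influence on the imputation of others. They do: the analysis takes data from all patients, and Step 2 conditions on all preceding scores. The weakness is that these scores are unmarked and outweighed.
- A reader might infer that this is the only analysis addressing discontinuation. The Protocol Synopsis gives the tipping point analysis that purpose, and Protocol 10.4.3.1 does not restrict its delta by reason for stopping. The restriction appears in SAP 5.7.1, and the two should be reconciled.
- A reader might quote a bias of 11% at Week 16 (0.15 × 0.75) or 23% at the 30% rate (0.30 × 0.75). These need three-quarters of stops to be for other reasons, complete loss of benefit and no retrieved scores at all. In that last case imputation from retrieved patients could not be run either. The 30% rate runs to Week 52, whereas the analysis is for Week 16 and, by extension, Week 44.

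Imputing from retrieved patients also has limits. With about 200 concurrent placebo patients for the Q8W contrast, 15% is 30 stoppers by Week 16. That leaves about 15 if half are retrieved, and fewer in the mFAS or at early visits.

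**Conclusion.** The concern holds in a limited form. Where off-drug scores are missing, the treatment policy analysis partly repeats the primary assumption, and nothing in the SAP tests stops for other reasons.

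With 15% stopping in each arm and benefit fully lost off drug, the bias favours fasinumab by about 0.03 to 0.08 of 1.1 points (3% to 8%) when half of stops are for other reasons and 0 to 50% of scores are retrieved. The upper bound is about 0.17, if every stop is for other reasons and nothing is retrieved. The bias is near zero if all stops are for adverse events, lack of efficacy or death, because equal errors cancel between arms. It is also near zero if about half the benefit persists and half of stops are for other reasons, and it can reverse.

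It would not change the Q4W versus placebo conclusion at the planned effect. It may matter more for Q8W versus placebo, where the SAP gives 42% and 46% mFAS power, but that was not quantified. The change is worth making before data lock because the analysis will be read by its label.

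**What to change.** In the treatment policy analysis only:

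1. Add an off-treatment indicator to the Step 2 regression, by arm where data allow, so that missing post-discontinuation scores are imputed from discontinued patients whose scores were retrieved.
2. Do not apply the Step 3 shift to living patients.
3. Pre-specify one fallback and the minimum count of retrieved patients per arm and visit that triggers it, for example an off-treatment term pooled across arms.
4. State separately how scores after death are handled. Without Step 3 or another rule, they would be modelled on living patients.

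Leave the primary analysis unchanged.

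The cost is SAP wording and one further imputation model. SAP section 1 allows revision before data lock. The downsides are a wider confidence interval for this analysis and reliance on the fallback where retrieved patients are few, as is likely for Q8W against concurrent placebo.

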### Tipping Point Analysis

Sensitivity analysis using a tipping point approach with multiple imputation will be performed to assess the robustness of the results due to data that may be missing not-at-random (MNAR).

This approach will introduce a sensitivity parameter,  $\delta$ . Estimations will be performed using multiple imputation methodology. Missing data up to week 52 timepoint will be imputed 50 times to generate 50 complete datasets by using SAS procedure PROC MI for each  $\delta$  following the 2 steps below:

- Step 1: The monotone missing pattern is induced by Markov Chain Monte Carlo (MCMC) method in MI procedure using seed number 4751611. If a randomly imputed score is imputed outside the range of the WOMAC subscale score of 0-10, then the algorithm will continue to randomly impute scores until one within the range of 0-10 is obtained.
- Step 2: The missing WOMAC subscale scores at visits subsequent to treatment discontinuation will be imputed using the regression method for the monotone pattern with seed number 4751611 and adjustment for covariates including treatment groups, randomization strata strata (K-L category [2 to 3, or 4], index joint [knee, hip], and geographical region [Europe, North America]), baseline WOMAC subscale score and all WOMAC subscale scores at preceding visits. Scores that are imputed outside the range of the WOMAC subscale will be addressed in the same manner as in step 1.
- Step 3: For missing data because of permanent study treatment discontinuation due to adverse events, death or lack of efficacy,  $\delta$  will be added to the imputed values ( $\delta = 0$  corresponds to the MAR assumption).

Each imputed data set will be analyzed using a MMRM model with terms for baseline WOMAC subscale score corresponding to the efficacy variable being analyzed, randomization strata (K-L category [2 to 3, or 4], index joint [knee, hip], and geographical region [Europe, North America]), treatment, visit, and treatment-by-visit interaction as fixed effects. For each  $\delta$  the SAS MIANALYZE procedure will be used to generate valid statistical inferences by combining results from the 50 analyses using Rubin's formula. By progressively increasing  $\delta$ , the sensitivity analysis will explore the tipping points, e.g.,  $\delta$  value when the p-value for a treatment comparison is above 0.025 or 0.05. Results will be then summarized using summary tables and graphs.

### Per Protocol Set Analysis

Sensitivity analyses based on the PPS will be performed using the same approach as specified for the primary analysis in the beginning of this section. Values of the stratifying variables utilized for analysis on the PPS will be those captured in the EDC system.

## USM Analysis

WOMAC pain and physical function will be summarized descriptively based on the USM Analysis set. No sensitivity analysis will be conducted using the USM analysis set.

### 5.7.2. Subgroup Analysis

Descriptive analyses by treatment group will be performed on both raw and change from baseline values for each visit for the WOMAC pain subscale score and physical function subscale scores to summarize the treatment effects across subpopulations defined by the following baseline characteristics:

- K-L category [2 to 3, or 4]
- Index joint [Knee, Hip]
- Region [Europe, North America]
- Age group [ $< 65$ , 65-74,  $\geq 75$  years]
- Sex [Male, Female]
- Weight group [ $<$  median baseline weight,  $\geq$  median baseline weight kg]
- BMI group [ $\leq$  median baseline BMI,  $>$  median baseline BMI]
- Flare status [Flare, Non-Flare] where flare patients are defined as patients who experience a  $\geq 1$  point increase in WOMAC pain scores from the Screening to the Baseline Visit.

An MMRM model analogous to that used for the primary analysis will be constructed, also including terms for subgroup and subgroup-by-treatment, subgroup-by-visit and subgroup-by-treatment-by-visit interactions as fixed effects. Multiple imputation will not be performed for the subgroup analyses. In addition to the actual change from baseline values, their LS means, differences of LS Means between treatment groups and corresponding 95% CIs within each subgroup at each visit will be presented. The p-value corresponding to the overall subgroup-by-treatment interaction will be supplied. Forest plots for the subgroup analyses will also be provided.

### 5.7.3. Analysis of Secondary Efficacy Variables

The key secondary variables defined in the study protocol are:

1. Change in the Patient Global Assessment (PGA) scores from baseline to week 16
2. Percentage of patients who had a response at week 16, with response defined as an improvement by  $\geq 30\%$  in the WOMAC pain subscale scores
3. Change in WOMAC pain subscale scores from baseline to week 44
4. Change in WOMAC physical function subscale scores from baseline to week 44
5. Change in the PGA scores from baseline to week 44
6. Change in WOMAC pain subscale scores from baseline to the average score across Weeks 4, 8, 12 and 16

7. Change in WOMAC physical function subscale from baseline to the average score across Weeks 4, 8, 12 and 16
8. Change in WOMAC pain subscale scores from baseline to the average score across Weeks 36, 40 and 44
9. Change in WOMAC physical function subscale scores from baseline to the average score across Weeks 36, 40 and 44

The following are secondary hypotheses specified in the study protocol that will be tested:

- H1,2: There is no treatment difference between fasinumab 1 mg Q4W and placebo in Patient Global Assessment score at week 16 versus there is treatment difference in Patient Global Assessment score at week 16
- H1,3: There is no treatment difference between fasinumab 1 mg Q4W and placebo in the proportion of patients with  $\geq 30\%$  improvement in the WOMAC pain subscale scores at week 16 versus there is treatment difference in proportion of patients with  $\geq 30\%$  improvement in WOMAC pain at week 16
- H1,4: There is no treatment difference between fasinumab 1 mg Q4W and naproxen in WOMAC pain subscale scores at week 16 versus there is a treatment difference in the WOMAC pain subscale scores at week 16
- H1,5: There is no treatment difference between fasinumab 1 mg Q4W and naproxen in WOMAC physical function subscale scores at week 16 versus there is a treatment difference in the WOMAC physical function subscale scores at week 16
- H1,6: There is no treatment difference between fasinumab 1 mg Q4W and placebo in WOMAC pain subscale scores at week 44 versus there is treatment difference in WOMAC pain subscale scores at week 44
- H1,7: There is no treatment difference between fasinumab 1 mg Q4W and placebo in WOMAC physical function subscale scores at week 44 versus there is treatment difference in WOMAC physical function subscale scores at week 44
- H1,8: There is no treatment difference between fasinumab 1 mg Q4W and placebo in Patient Global Assessment score at week 44 versus there is treatment difference in Patient Global Assessment score at week 44
- H1,9: There is no treatment difference between fasinumab 1 mg Q4W and naproxen in Patient Global Assessment score at week 16 versus there is treatment difference in Patient Global Assessment score at week 16
- H1,10: There is no treatment difference between fasinumab 1 mg Q4W and placebo in the WOMAC pain subscale scores averaged across Weeks 4, 8, 12 and 16 versus there is treatment difference in the WOMAC pain subscale scores averaged across Weeks 4, 8, 12 and 16
- H1,11: There is no treatment difference between fasinumab 1 mg Q4W and placebo in the WOMAC physical function subscale scores averaged across Weeks 4, 8, 12 and 16

16 versus there is treatment difference in the WOMAC physical function subscale scores averaged across Weeks 4, 8, 12 and 16

- H1,12: There is no treatment difference between fasinumab 1 mg Q4W and placebo in the WOMAC pain subscale scores averaged across Weeks 36, 40 and 44 versus there is treatment difference in the WOMAC pain subscale scores averaged across Weeks 36, 40 and 44
- H1,13: There is no treatment difference between fasinumab 1 mg Q4W and placebo in the WOMAC physical function subscale scores averaged across Weeks 36, 40 and 44 versus there is treatment difference in the WOMAC physical function subscale scores averaged across Weeks 36, 40 and 44
- H1,14: There is no treatment difference between fasinumab 1 mg Q4W and naproxen in WOMAC pain subscale scores at week 44 versus there is treatment difference in WOMAC pain subscale scores at week 44
- H1,15: There is no treatment difference between fasinumab 1 mg Q4W and naproxen in WOMAC physical function subscale scores at week 44 versus there is treatment difference in WOMAC physical function subscale scores at week 44
- H1,16: There is no treatment difference between fasinumab 1 mg Q4W and naproxen in the proportion of patients with  $\geq 30\%$  improvement in the WOMAC pain subscale scores at week 16 versus there is treatment difference in proportion of patients with  $\geq 30\%$  improvement in WOMAC pain at week 16
- H2,2: There is no treatment difference between fasinumab 1 mg Q8W and placebo in Patient Global Assessment score at week 16 versus there is treatment difference in Patient Global Assessment score at week 16
- H2,3: There is no treatment difference between fasinumab 1 mg Q8W and placebo in the proportion of patients with  $\geq 30\%$  improvement in the WOMAC pain subscale scores at week 16 versus there is treatment difference in proportion of patients with  $\geq 30\%$  improvement in WOMAC pain at week 16
- H2,4: There is no treatment difference between fasinumab 1 mg Q8W and naproxen in WOMAC pain subscale scores at week 16 versus there is a treatment difference in the WOMAC pain subscale scores at week 16
- H2,5: There is no treatment difference between fasinumab 1 mg Q8W and naproxen in WOMAC physical function subscale scores at week 16 versus there is a treatment difference in the WOMAC physical function subscale scores at week 16
- H2,6: There is no treatment difference between fasinumab 1 mg Q8W and placebo in WOMAC pain subscale scores at week 44 versus there is treatment difference in WOMAC pain subscale scores at week 44
- H2,7: There is no treatment difference between fasinumab 1 mg Q8W and placebo in WOMAC physical function subscale scores at week 44 versus there is treatment difference in WOMAC physical function subscale scores at week 44

- H2,8: There is no treatment difference between fasinumab 1 mg Q8W and placebo in Patient Global Assessment score at week 44 versus there is treatment difference in Patient Global Assessment score at week 44
- H2,9: There is no treatment difference between fasinumab 1 mg Q8W and naproxen in Patient Global Assessment score at week 16 versus there is treatment difference in Patient Global Assessment score at week 16
- H2,10: There is no treatment difference between fasinumab 1 mg Q8W and placebo in the WOMAC pain subscale scores averaged across Weeks 4, 8, 12 and 16 versus there is treatment difference in the WOMAC pain subscale scores averaged across Weeks 4, 8, 12 and 16
- H2,11: There is no treatment difference between fasinumab 1 mg Q8W and placebo in the WOMAC physical function subscale scores averaged across Weeks 4, 8, 12 and 16 versus there is treatment difference in the WOMAC physical function subscale scores averaged across Weeks 4, 8, 12 and 16
- H2,12: There is no treatment difference between fasinumab 1 mg Q8W and placebo in the WOMAC pain subscale scores averaged across Weeks 36, 40 and 44 versus there is treatment difference in the WOMAC pain subscale scores averaged across Weeks 36, 40 and 44
- H2,13: There is no treatment difference between fasinumab 1 mg Q8W and placebo in the WOMAC physical function subscale scores averaged across Weeks 36, 40 and 44 versus there is treatment difference in the WOMAC physical function subscale scores averaged across Weeks 36, 40 and 44

The hypotheses H1,4, H1,5, H1,6, H1,7, H1,14 and H1,15 can be tested within the same analysis method used to test H1,1 as described in Section 5.7.1. Similarly, H2,4, H2,5, H2,6 and H2,7 can be tested within the same analysis methods used to test H2,1 as described in Section 5.7.1. Additionally, the treatment policy analysis, per-protocol analysis and subgroup analyses described in Section 5.7.1 for the primary endpoint can also be utilized for the hypotheses mentioned in this paragraph.

To test H1,2, H1,8 and H1,9, a method analogous to that used to test H1,1 in Section 5.7.1 can be utilized, replacing the respective WOMAC subscale score with the PGA score. Likewise, H2,2, H2,8 and H2,9 can be tested using a method analogous to that used to test H2,1 in Section 5.7.1, replacing the respective WOMAC subscale score with the PGA score and only using the subset of patients in the mFAS randomized after protocol amendment 5 for the analyses. The multiple imputation algorithm will be modified to resample values outside the range of the PGA score (0-5) in a manner similar to the primary analysis.

To test H1,3 and H1,16, Cochran Mantel Haenszel (CMH) approach stratified by the randomization strata (K-L category [2 to 3, or 4], index joint [knee, hip], and geographical region [Europe, North America]) will be used with missing data considered as non-response. The same method can be utilized to test H2,3, however, only basing the analysis on the subset of patients in the mFAS who were randomized post protocol amendment 5.

[figure not shown]
To test hypothesis  $H_{1,10}$ ,  $H_{1,11}$ ,  $H_{1,12}$  and  $H_{1,13}$ , the same multiple imputation method used to test  $H_{1,1}$  in Section 5.7.1 will be utilized. However, the analysis model for the average of the WOMAC subscale scores across multiple visits will instead be an ANCOVA model with terms for baseline WOMAC subscale score, randomization strata (K-L category [2 to 3, or 4], index joint [knee, hip], and geographical region [Europe, North America]) and treatment. Hypothesis  $H_{2,10}$ ,  $H_{2,11}$ ,  $H_{2,12}$  and  $H_{2,13}$  will be tested via an analogous method using only the subset of patients in the mFAS randomized after protocol amendment 5 for the analyses.

